## 4. STATISTICAL ANALYSES

### 4.1. General Considerations

#### 4.1.1. General Methodology

If participants prematurely discontinue the study for non-safety reasons prior to Day 8 (primary endpoint), additional replacement participants may be enrolled at the discretion of the sponsor and investigator. These replacement participants will be assigned to the same treatment sequence and same dose as the corresponding participant who prematurely discontinued from the study. Participants will not be replaced if the reason for discontinuation from the study is due to a safety concern.

Data will be summarized by dose of VH3739937 and placebo, unless otherwise specified.

Data will be summarized either by visit or for the study intervention period and overall (i.e., study intervention period plus cART period) separately, as appropriate for each endpoint.

For all endpoints, except for ECG, the baseline value will be the latest pre-dose assessment with a non-missing value, including those from unscheduled visits. Day 1 pre-dose ECGs will be

performed in triplicate and the average of pre-dose triplicate measurements will be used as baseline.

Continuous and categorical variables will be summarized using the following descriptive statistics, unless otherwise specified:

- Continuous data: n (number of participants used for the summary), arithmetic mean, SD, median, interquartile range, minimum and maximum. For PK data, geometric mean, SD of log-transformed data and geometric %CVb may also be used.
- Categorical data: number and percentage of participants.

PK values collected outside analysis visit windows will be excluded from data summaries (applies to both Tables and Figures) but will be included in listings. Figures with subject level information will include all values (i.e. irrespective of being within/outside of analysis visit windows). Confidence intervals for PK data summaries will use 95% confidence levels, unless otherwise specified.

Only lab data from central laboratory will be included in lab data summaries. Lab data from local laboratories, if any, will be included in listings (and flagged appropriately).

No imputation for missing values will be performed.

Subject level data will be available through the Reporting & Analysis Plan Improving Design and Delivery of Outputs Data Viewer (RAPIDO DV) tool. Only selected listings required by regulatory agencies will be created in static fashion. See OPS for the list of selected listings.

#### **4.1.2. Baseline Definition**

For all endpoints, the baseline value will be the latest pre-dose assessment with a non-missing value, including those from unscheduled visits. If time is not collected, Day 1 assessments are assumed to be taken prior to first dose and used as baseline. If Day 1 pre-dose ECG has been assessed more than once (e.g. in triplicate), the average of the available ECG measurements will be used as baseline value.

Unless otherwise stated, if baseline data is missing, no derivation will be performed, and baseline will be set to missing.

Baseline will not be rederived for the Follow-Up period.

### **4.2. Primary Endpoint(s) Analyses**

#### **4.2.1. Definition of endpoint(s)**

Plasma HIV-1 RNA values (copies/mL) will be used for the primary efficacy analysis. Change from baseline at the time point where the HIV-1 RNA is minimum (nadir) during the treatment period will be calculated for each participant in the original and log10 scales. The change from baseline at nadir is the primary endpoint used to construct the primary estimand (see Section 1.1.1). According to primary estimand definition (Section 1.1.1), if cART medication starts prior to Day 8 (for any reason), change from baseline values after cART initiation will be excluded from calculation of change from baseline at nadir.

Note, the change from baseline at nadir during monotherapy is typically the maximum change from baseline in HIV-1 RNA, or in other words the maximum Viral Load Decline (VLD). However, for participants who have all their post-baseline HIV-1 RNA values during treatment higher than the baseline value (e.g. as is the potential with some participants randomized to

placebo) the change from baseline at nadir is the minimum change from baseline. Also, if a (placebo) participant has a high increase from baseline in HIV-1 RNA and then a smaller decrease from baseline (or vice versa), the maximum change from baseline is at the point where HIV-1 RNA is its peak (zenith); the change from baseline at nadir will be used in this case in the primary analysis. From now on, in this document by “maximum change from baseline in HIV-1 RNA” during treatment we will mean the “change in HIV-1 RNA at nadir”.

The log10 transformation is used to allow for comparisons with data publicly available in the same scale from other compounds, and hence aid in interpretation.

#### **4.2.2. Main analytical approach**

The primary efficacy analysis will be based on the Full Analysis Set.

Maximum change from baseline in plasma HIV-1 RNA during monotherapy will be summarized in original and log10 scale using descriptive statistics as described in Section [4.1.1](#).

Any missing HIV-1 RNA data (e.g., due to missed visits in the clinic, LFU or for any other reason) will not be imputed and will remain missing. Whatever HIV-1 RNA data are available for a participant during part-1 study and prior to starting cART will be used to calculate maximum VLD. Participants who withdraw from study prior to the end of the treatment period, preventing assessment of primary endpoint, no imputation will be performed for missed assessments after their study withdrawal.

All HIV-1 RNA data from all participants will be included in a listing.

#### **4.2.3. Sensitivity analyses**

The primary analysis described in Section [4.2.2](#) will be repeated on the PP analysis set, and on the Safety analysis set if any participant receives treatment other than the one to which was randomized.

None of the IEs specified for the primary estimand are applicable for the PP analysis set, as none of them can occur in participants within the PP analysis set (because of criteria in [Table 1](#)). All available HIV-1 RNA data from the monotherapy period on the PP analysis set will be used for the sensitivity analysis.

#### **4.2.4. Supplementary analyses**

##### **4.2.4.1. Summaries of HIV-1 RNA Change from Baseline by Visit**

Change from baseline in plasma HIV-1 RNA will be calculated for each participant at each assessment time point during the monotherapy and Follow-Up periods in the original and log10 scales. Change from Baseline at each assessment time point during monotherapy and Follow-Up will be summarized in original and log10 scale using descriptive statistics as described in Section [4.1.1](#).

Mean and 95% CI of change from baseline in plasma HIV-1 RNA in the log10 scale will be plotted by visit for the monotherapy period.

These analyses will be performed on the FAS, PP analysis set, and Safety analysis set if any participant receives treatment other than the one to which they were randomized.

#### 4.2.4.2. Modelling of HIV-1 RNA Change from Baseline

A mixed-effects linear model will be fitted using plasma HIV-1 RNA change from baseline (on log10 scale) during the Study Intervention Period Days 1-7 period from all treatment arms as the outcome measure, with day, treatment, day and treatment interaction and baseline HIV-1 RNA (on log scale) as main effects and participant as a random effect. Day will be treated as continuous variable. The Kenward & Roger (KR2) degrees of freedom approach will be used [Kenward & Roger, 2009]. The model will be used to estimate the rate of decline in HIV-1 RNA and its 90% CI for each treatment.

Model assumptions will be examined by obtaining a normal probability plot of the residuals and a plot of the residuals versus the fitted values (i.e. checking the normality assumption and constant variance assumption of the model respectively) to gain confidence that the model assumptions are reasonable.

If there are departures from model assumptions, or if the model fails to converge, or if parameter estimates are at the boundary of parametric space (e.g. zero variance estimates), or if the model does not fit the data well, alternative models or data transformations may be explored. For example, if model fit is poor, as e.g. may be the case if the HIV-1 RNA does not decline linearly over time, the same model treating day as categorical (with an autoregressive order one (AR(1)) covariance structure for the residuals (R matrix) or simpler structure (e.g.  $R = \sigma^2 I$ )) may be used, or the same model using a variable transformation for day or a model using splines may be used. In case day is treated as categorical, mean estimates of change from Baseline at each (or selected) day for each treatment will be provided along with 90% CIs.

This analysis will be performed on the FAS, PP analysis set, and Safety analysis set if any participant receives treatment other than the one to which was randomized.

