1.3. Schedule of Activities

Table 1 SoA

| Procedure ¹ | Screening ² (7-14 days before Day 1) | Study Intervention Period Days 1-7 | | | | | | Post-Study Intervention Follow-up Days 8-21 | | | | Follow-up/ED ¹⁵ | Notes ED = early discontinuation/withdrawal | |
|---|--|------------------------------------|----------------|---|-----------------------|---|-----------------------|---|----------------|-----------------------|-----------------------|----------------------------|--|---|
| | | Day 1 | Day 2 | Days 3 and 4 1 clinic visit and 1 virtual ³ | | Days 5 and 6 1 clinic visit and 1 virtual ³ | | Day 7 | Day 8 | Day 14 (+/- 1 day) | Day 21 (+/- 1 day) | Day 25 (+/- 1 day) | | |
| | | Clinic visit 1 | Clinic visit 2 | Clinic visit 3 | Virtual ¹⁴ | Clinic visit 4 | Virtual ¹⁴ | Clinic visit 5 | Clinic visit 6 | Clinic visit 7 | Clinic visit 8 | Clinic visit 9 | | |
| Outpatient Visit | X | X | X | X | | X | | X | X | X | X | X | | |
| Video/phone call | | | | | X | | X | | | | | | | |
| Informed consent | X | | | | | | | | | | | | | See Section 10.1.3 for details |
| Inclusion and exclusion criteria | X | X | | | | | | | | | | | | Recheck clinical status before 1 st dose of study medication. See Section 5.1 and Section 5.2 for Inclusion and Exclusion criteria |
| Demography | X | | | | | | | | | | | | | See Section 8.1.1 for more information |
| Medical history (includes substance usage and Family history of premature CV disease) | X | | | | | | | | | | | | | Substances: Drugs and Alcohol Premature CV disease: female participant < 65 years or male participant < |

CONFIDENTIAL

212580

Protocol Amendment 1 Final

| Procedure ¹ | Screening ² (7-14 days before Day 1) | Study Intervention Period Days 1-7 | | | | | | Post-Study Intervention Follow-up Days 8-21 | | | Follow-up/ED ¹⁵ | Notes ED = early discontinuation/withdrawal | |
|---|--|------------------------------------|----------------|---|-----------------------|---|-----------------------|---|----------------|-----------------------|----------------------------|--|---|
| | | Day 1 | Day 2 | Days 3 and 4 1 clinic visit and 1 virtual ³ | | Days 5 and 6 1 clinic visit and 1 virtual ³ | | Day 7 | Day 8 | Day 14 (+/- 1 day) | Day 21 (+/- 1 day) | | |
| | | Clinic visit 1 | Clinic visit 2 | Clinic visit 3 | Virtual ¹⁴ | Clinic visit 4 | Virtual ¹⁴ | Clinic visit 5 | Clinic visit 6 | Clinic visit 7 | Clinic visit 8 | | |

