9.5.1. Sample Size Considerations

Based on data from the short-term monotherapy study of the BMS-955176/GSK3532795 proof of concept study (AI468002), the GSK2838232 proof of concept study, and the GSK3640254 proof of concept study (208132), the distribution of maximum change from baseline VLD values on the log scale can be assumed to be normal.

Assuming normality, the sample size of N=6 participants per intervention cohort allows estimation of the mean maximum VLD in log10 scale with precision shown on [Table 9](#) shows the expected precision of the estimated mean maximum VLD in log10 scale measured by the 95% CI width for various observed data variability assumptions as reflected by the sample SD.

[figure not shown]
Table 9 Expected precision (measured by the 95% CI width) of the estimated mean of maximum VLD in log10 scale for various assumptions of observed data variability for N = 6 participants

| Sample SD | Precision (95% CI Upper Limit) |
|-----------|-----------------------------------|
| 0.40 | 0.84 |
| 0.50 | 1.05 |
| 0.65 | 1.36 |
| 0.80 | 1.68 |

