## 1.2. Study Design

CCI

Design Features	

Phase IIa, PoC, multi-center, randomized, double-blind (sponsor unblinded), placebo-controlled adaptive study

Orally administered VH3739937 over 7 days in treatment naive HIV-1 infected adults

The study will evaluate the antiviral effect, safety, tolerability and PK/PD of VH3739937

Participants have a Screening visit approximately 7 to 14 days prior to first dose on Day 1

This study will be conducted in two parts:

Part 1: 20 TN HIV-1 infected adults will be randomized to one of 4 cohorts.

Part 2: 7 TN HIV-1 infected adults will be randomized to active treatment or placebo.

-----------------	--

Overview of Study Design and Key Features				
	
 
• Total duration of study participation is approximately 32 to 53 days based on the following: 
 
◦ 7 to 14 days, with a maximum of 28 days permitted for screening/qualification period
 
◦ 7 days for treatment with the study intervention and assessment at all planned visits
 
◦ 18 days for post-study intervention follow up visits including the final follow up visit. Participants will take cART throughout this period.
 
 
 
			
Study intervention	Part	Cohort Number	Number of Participants	Intervention
	1A	1	1	Placebo CCI [REDACTED]
		2	6	VH3739937 CCI [REDACTED] CCI [REDACTED]
		3	6	VH3739937 CCI [REDACTED] CCI [REDACTED]
	1B	1	1	Placebo CCI [REDACTED]
		4	6	VH3739937 CCI [REDACTED]
		2	1	Placebo CCI [REDACTED]
		5	6	VH3739937 CCI [REDACTED] CCI [REDACTED]
Study intervention Assignment	
 
• Part 1a: cohort 1 (placebo), cohort 2 or cohort 3 in a 1:6:6 ratio
 
• Part 1b: cohort 1 (placebo) or cohort 4 in a 1:6 ratio
 
• Part 2: cohort 1 (placebo) or cohort 5 in a 1:6: ratio.
 
			
Interim Analysis	
 
• An informal interim analysis will be conducted using available preliminary unvalidated in-stream unblinded clinical data once all participants (to include a minimum of 5 participants per active arm and 2 placebo participant) from Part 1 have, at a minimum, completed their Day 8 visit.
 
			

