#### 4.6.2.1. Estimation of Accumulation Ratios

Accumulation ratios may be estimated for  $C_{max}$  and  $AUC_{0-24}$  when more than one dose is administered during the monotherapy period, following guidance from CPMS prior to final database lock.

Accumulation ratios are defined as the ratio of PK parameters from the last administration to Day 7 as follows:

$$R(PK \text{ parameter}) = \frac{\text{PK parameter on Day of last administration}}{\text{PK parameter on Day 1}},$$

$$\text{e.g. } R(C_{max}) = \frac{C_{max} \text{ on Day of last administration}}{C_{max} \text{ on Day 1}}.$$

To estimate the accumulation ratios for each treatment, a mixed-effects ANOVA model will be used on the loge-transformed PK parameters, with a random intercept (for each participant) and fixed effects for the day. Day will be treated as a categorical variable in the model. The Kenward & Roger (KR2) degrees of freedom approach will be used

[Kenward & Roger, 2009]. The accumulation ratio will be estimated by calculating the ratio of the geometric least squares (GLS) means of PK parameters between last administration and first administration and the corresponding 90% CI. The GLS means of PK parameters on first administration and last administration, along with the estimated accumulation ratio and its 90% CI will be displayed. No imputation will be done for missing PK parameters.

For each of the statistical models distributional assumptions underlying the model used for analysis will be examined by obtaining a normal probability plot of the residuals and a plot of the residuals versus the fitted values (i.e. checking the normality assumption and constant variance assumption of the model respectively) to gain confidence that the model assumptions are reasonable.

If there are any departures from model assumptions, alternative models or data transformations may be explored.

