### **6.3. Appendix 2 Data Derivations Rule**

#### **6.3.1. Study Period**

Assessments and events will be classified according to the time of occurrence relative to the study intervention period.

**Pre-Treatment** is defined as time prior to the first dose of study intervention.

**On-Treatment Period Days 1-8** is defined as time from first study intervention dose (typically Day 1) to start of cART treatment (typically Day 8).

- If time of assessment or time of study intervention is not collected, Day 1 assessments other than AEs are considered to have occurred prior to study intervention dose and therefore considered on Pre-Intervention period, whereas AEs with Day 1 onset are considered to have occurred after study intervention dose and therefore considered on Monotherapy period.

**Post-Treatment Period Days 8- 25** is defined as time from first dose of cART treatment until study completion or withdrawal

- If time of assessment or time of cART initiation is not collected, Day 8 assessments other than AEs are considered to have occurred prior to cART initiation and therefore considered on on-treatment period, whereas AEs with Day 8 onset are considered to have occurred after cART initiation and therefore considered on Follow-Up period.

For concomitant medications, study periods will be defined as follows:

	Pre-Treatment	Monotherapy	Follow-Up	Pre-Treatment	cART	Follow-Up
(a)	x—x			Y	N	N
(b)	x	—x		Y 	Y 	N
(c)	x	—	—x	Y 	Y 	Y 
(d)		x—x		N	Y 	N
(e)		x—	—x	N	Y	Y
(f)			x—x	N	N	Y
(g)	?—x			Y	N	N
(h)	?	—x		Y*	Y	N
(i)	?	—	—x	Y*	Y*	Y*
(j)	x	—	?	Y	Y**	Y**
(k)		x—	?	N	Y	Y**
(l)			x—?	N	N	Y
(m)	?	—	?	Y***	Y***	Y***
(n)	x	x		Y	Y	N
(o)	?	x		Y	Y	N
(p)		x—x		N	Y	N
(q)	x	—	x	N	Y 	Y
(r)		x	—?	N	N	Y**
(s)		x	—x	N	N	Y
(t)	x	x		N	Y	Y

x = start/stop date of medication

? = missing start/stop date of medication

\* If a medication is stopped during the Monotherapy period or during the Follow-Up period and no start date is recorded it will be assumed that the medication was ongoing from the Pre-Intervention period

\*\* If a medication is started Pre-Intervention or on Monotherapy and no stop date is recorded then usage will be assumed to be ongoing for the remainder of the study

\*\*\* If a medication has no start or stop date it will be assumed that the medication was ongoing from the Pre-Intervention period to the Follow-Up period

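### The HIV-1 RNA slope model has no participant-level slope, so its 90% CIs are too narrow if participants decline at different rates; it also leaves out the pre-cART Day 8 value

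*SAP*

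**What the plan says.** SAP 4.2.4.2 fits a linear mixed model to log10 change from baseline. Day is continuous, and the terms are day, treatment, "day and treatment interaction and baseline HIV-1 RNA (on log scale) as main effects and participant as a random effect". The purpose is explicit: "The model will be used to estimate the rate of decline in HIV-1 RNA and its 90% CI for each treatment". Kenward-Roger (KR2) degrees of freedom are used.

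The SAP's other mixed model, for accumulation ratios in 4.6.2.1, spells out its random part: "with a random intercept (for each participant) and fixed effects for the day".

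Model assumptions are checked with a normal probability plot and a plot of residuals against fitted values. If the fit is poor, other models may be explored. The examples given are categorical day with AR(1) or simpler residuals, transformed day, and splines.

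The data are changes "during the Study Intervention Period Days 1-7 period from all treatment arms as the outcome measure". The SAP's on-treatment period (6.3.1), however, "is defined as time from first study intervention dose (typically Day 1) to start of cART treatment (typically Day 8"), and untimed Day 8 assessments other than AEs are placed before cART. Protocol 4.1 starts cART only after the Day 8 assessments. The primary endpoint runs through Day 8. The protocol's schedule of activities instead puts Day 8 under a column headed "Post-Study Intervention Follow-up Days 8-21".

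**The concern.** A random intercept lets participants differ in level but gives everyone in an arm the same slope. When slopes do differ, the uncertainty of an arm's mean slope comes mainly from having only 6 participants. The intercept-only model instead treats slope differences as residual noise, independent between visits, and averages them over all within-participant degrees of freedom. KR2 corrects small-sample inference under the covariance that was specified. It does not supply a missing variance component.

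Each dose's rate of decline could therefore look better determined than 6 participants can support.

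The Day 8 question is separate. The last pre-cART sample is the furthest in time and carries much of the information about a slope. Dropping it loses precision but does not itself make the interval too narrow.

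**Working it through.** **The plan's own precision figure.** Protocol Table 9 gives the 95% CI width for a mean of 6 as 2 × t(0.975, 5) × SD/√6 = 2 × 2.571 × SD/2.449 = 2.10 × SD. For SD 0.40, 0.50, 0.65 and 0.80 this is 0.84, 1.05, 1.36 and 1.68, as printed. No such figure is given for the slope.

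**Inputs**
- Arms (SAP 1.2): Part 1 has three active cohorts of 6 and 2 placebo participants. For Part 2, "Part 2: 7 TN HIV-1 infected adults will be randomized to active treatment or placebo", split 6 and 1. The total is four active arms of 6 plus 3 placebo, or 27 participants in 5 arms.
- Post-baseline visits in the window (Protocol 1.3): Day 2, Day 3 or 4, Day 5 or 6, Day 7. These are set to 2, 3.5, 5.5 and 7.
- SD of the Day 8 change: Table 9 values, which the protocol gives "for various observed data variability assumptions as reflected by the sample SD". They refer to maximum viral load drop and serve here as a proxy.
- Assay SD *s*: not in the documents. Assumed 0.20 log10, range 0.15-0.25.
- Share *f* of between-participant variance that lies in the slope: not in the documents. Shown from 0 to 100%.

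**Formulas**
- Between-participant variance V = SD² − 2s², removing assay error at baseline and at Day 8.
- Slope variance τ² = f × V/49 (7 days from Day 1 to Day 8). The rest of V goes to the intercept.
- Sxx for Days 2, 3.5, 5.5, 7 (mean 4.5): 6.25 + 1 + 1 + 6.25 = 14.5.
- True variance of an arm's mean slope: (τ² + s²/Sxx)/6.
- Intercept-only model: MSE/(6 × Sxx) with 27 × 3 − 5 = 76 df. Slope deviations occupy 27 − 5 = 22 of those df, so MSE averages s² + (22/76) × Sxx × τ².

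**Worked case: SD 0.65, s = 0.20, f = 25%**
- V = 0.4225 − 0.08 = 0.3425; τ² = 0.25 × 0.3425/49 = 0.00175.
- True SE = √[(0.00175 + 0.04/14.5)/6] = 0.0274 log10/day.
- Average MSE = 0.04 + (22/76) × 14.5 × 0.00175 = 0.0473; reported SE = √(0.0473/87) = 0.0233.
- The ratio is 0.85, so the multiplier t(0.95, 76) = 1.665 acts like 1.42, which covers about 84%.

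**Simulation** (6,000 replicates per cell, s = 0.20, nominal 90%)

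| Slope share | Coverage, SD 0.50 | Coverage, SD 0.65 | 7-day half-width at SD 0.65: intercept-only v participant slopes (22 df) |
|---|---|---|---|
| 0% | 90% | 90% | 0.25 v 0.25 |
| 10% | 89% | 87% | not tabulated |
| 25% | 86% | 84% | 0.27 v 0.33 |
| 50% | 84% | 80% | 0.29 v 0.38 |
| 100% | 80% | 75% | 0.33 v 0.48 |

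Over SD 0.40-0.80 and assay SD 0.15-0.25, intercept-only coverage is 77-89% at a 25% share, 72-89% at 50% and 68-88% at 100%. Intervals built from participant slopes covered 89-91% in every cell.

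**REML check** with mixed visit days and a baseline covariate (250 fits × 4 arms, s = 0.20), at slope shares 0/25/50/100%:
- Intercept-only: 88/86/85/82% (SD 0.50) and 90/85/79/75% (SD 0.65).
- Random intercept plus slope, with 22 df approximating KR2: 94/92/92/93% and 97/93/91/90%.

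**Day 8.** Adding it moves the mean day to 5.2 and Sxx to 10.24 + 2.89 + 0.09 + 3.24 + 7.84 = 24.3. With equal slopes, leaving it out raises the slope SE by √(24.3/14.5) = 1.29, or 29%. With slope variation the ratio is √[(τ² + s²/14.5)/(τ² + s²/24.3)]. At SD 0.50-0.65 and s = 0.20 the increase is 15-20% at a quarter share, 10-15% at half and 6-10% if all the variance is in the slope.

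Adding Day 8 while keeping only the intercept lowers coverage at SD 0.65 to 80/73/68% at shares 25/50/100%, against 84/80/75% without it. The assay part of the error shrinks and the ignored slope part does not.

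**The case against.** The strongest reply is that the harm is conditional. No passage gives a slope variance or assay SD, the Table 9 SDs belong to another quantity, and with equal slopes the interval is nominal. At low SD, or where little of the variance is in the slope, the loss is a point or two. The REML coverages rest on about 1,000 intervals each, so differences of that size there mean little. This stands, and is why ranges are shown.

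The SAP also never says intercept only, and its fallback list is open-ended, so a random slope is permitted. That is true, but permission is not specification. The trigger is poor fit, the two plots do not target slope differences between participants, and the named alternatives address curvature or residual structure. How well those plots would detect slope variation was not calculated.

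The random-slope fit is itself conservative when slopes are equal (94-97% coverage), so it is not free in that case. The combined rule of fitting it and then falling back was not simulated.

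Finally, the analysis is supplementary, with no hypothesis test and no planned between-arm contrast. The by-visit means with 95% CIs already show between-participant precision and use Day 8. That limits the reach but does not make the slope intervals right.

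**Conclusion.** The concern holds. On its natural reading, SAP 4.2.4.2 gives slope intervals that are correct only if participants within an arm decline at the same rate. With assay SD 0.20 and SD 0.50-0.65, actual coverage of the 90% interval is 84-86% when a quarter of the between-participant variance is in the slope, and 75-80% when all of it is. These figures rest on an assumed assay SD, an assumed slope share and Table 9 SDs used as a proxy. The direction of the error does not depend on them, provided slopes vary.

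Omitting Day 8 is a precision loss only, of 6-29% in the true slope SE at SD 0.50-0.65. The documents also disagree on which period Day 8 belongs to, so the SAP needs to state the rule. The point should be fixed before the final analysis. The primary nadir summary is not affected.

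**What to change.** In SAP 4.2.4.2:
- Replace the participant random effect with a random intercept and random slope for day, by participant.
- If that model does not converge, or the slope variance is on the boundary, compute each participant's least-squares slope. Report the arm mean with a t interval based on between-participant variation, either pooled across arms (22 df with 27 participants) or with n − 1 df within arm. Going straight to this method would also be acceptable: it held 89-91% coverage throughout and costs almost no width when slopes are equal.
- State that all post-baseline values before cART, through Day 8, enter the model.

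Make the changes together, since adding Day 8 to an intercept-only model worsens coverage.

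The cost is SAP wording and a few lines of code, with no change to trial conduct. Intervals will be wider where slopes differ, and the random-slope fit is somewhat conservative where they do not. Because SAP 4.7 records that the unblinded interim on Part 1 (20 of the 27 participants) has taken place and that the statistician's role has unblinded access, the amendment should be dated and should give this reason for the change.
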